Official Study Title:

Flexible representation of speech in the supratemporal plane

NCT Number:

NCT05209386

Document:

Statistical Analysis Plan

Document Date:

July 15, 2020

STATISTICAL DESIGN AND POWER ANALYSIS

Statistical Design, Power and Analytic Approach. We will test neurosurgical patients (ages 15-25 years) undergoing evaluation and treatment who require chronic (>7 d) sEEG implantation and recording of the temporal lobe for seizure localization or brain mapping. One set of behavioral tasks, and corresponding electrophysiological measures, will allow us to address Aim 1. Another will address Aim 2. Patient permitting, our goal is to have the same patient complete all tasks. All participants will undergo neuropsychological tests and will have detailed history/demographic information as part of their clinical battery.

Power and Sample Size. Robust behavioral effects will allow examination of perceptual weights in neural representation. Using behavioral effect sizes from **Figure 2** pilot data to estimate the sample size required for a predicted power of 0.8 (two-tailed alpha at .05) yields a sample of N=25. This leaves open the issue of power for neural measures. Our pilot EEG data with the same task/stimuli revealed robust effects with N=23 (**Figure A**), reassuring that N=25 is a reliable target for EEG. The SNR advantages of sEEG versus EEG, and our sEEG pilot data in **Figure 3**, suggest that this sample size will be more than sufficient for sEEG measures, especially as they will be utilized in a within-patient/within-electrode experimental design.

Analyses. Specific pre-registered analyses will assess the hypotheses outlined in the Approach section of the proposal. Specifically, we will test the following hypotheses:

(**H1**) broadly, the relative perceptual weight of VOT and F0, as measured behaviorally, will be reflected in cortical response, (**H2**) with modulation as a function of baseline perceptual weights, (**H3**) shifts experimentally invoked by a change in listening context by presenting speech in noise, (**H4**) and by introducing an 'accent' that shifts short-term input regularities across VOT and F0. In the latter case, our approach will allow us to test the specific directional hypothesis (**H5**) that F0 perceptual weights in the DBSL paradigm are both exaggerated by Canonical input regularities that cleanly convey a VOTxF0 correlation consistent with English and that F0 perceptual weights are down-weighted upon introduction of a regularity that violates the typical pattern of English (supported by scalp EEG pilot, **Figure A**). Our use of sEEG allows us to evaluate these hypotheses across the supratemporal plane thereby testing the strong, and falsifiable, hypothesis (**H6**) that adaptive plasticity effects are present in HG versus (**H7**) apparent only at higher levels of the cortical hierarchy. Our ability to test these hypotheses is complemented by sEEG electrode placement in cortical regions outside STP (see **Figure 3**) which will support secondary hypotheses and serve as control electrode sites.

The study design is justified our extensive behavioral research demonstrating the feasibility of the project rationale. On the electrophysiological side, our pilot data (**Figures A,3**) demonstrate the feasibility of recording robust sEEG and EEG signals responsive to the acoustic dimensions we manipulate. This will provide clear, informative, interpretable data with which to evaluate the hypotheses listed above.

Evaluating the Hypotheses: Behavioral Analyses. We will evaluate the behavioral impact of the VOT and F0 acoustic dimensions on classification using *mixed-effects logistic regression* (with patient as a random effect, stimulus VOT and F0 as fixed effects and classification responses as the outcome). Following our prior work,^{14,25-29} perceptual weights for the dimensions will be computed for each patient as the correlation between dimension values and the proportion of *peach* classifications across all stimuli in the VOTxF0 stimulus grid with absolute values of the correlation coefficients normalized to sum to one as an *index of relative perceptual weight* in quiet (Aim 1) and in noise (Aim 2). To examine the impact of a change in 'accent' in the DBSL paradigm, we will use mixed logit models with responses as a function of patient, block, test stimulus F0 and the interaction between block and F0 (Aim 2). Patient will be modeled as a random effect, with the other factors as fixed effects.

Evaluating the Hypotheses: Neural Analyses. We will take a multi-pronged analysis approach. Our pilot data in **Figure 3** demonstrate that *high-y* activity (HGA) is modulated by graded acoustic details across the VOT and F0 dimensions across electrodes placed in the STP. Following the analysis pipeline used in our pilot data analyses, we will specifically examine stimulus-time-locked HGA to the *Test* stimuli, which possess consistent, perceptually-ambiguous VOT and differentiated F0. We have specific, directional predictions (detailed above)

regarding how HGA to F0-differentiated *Test* stimuli will vary according to perceptual weight in behavior. To briefly recap, we expect that HGA to *Test* stimuli will be better differentiated (1) in the Speech-in-Noise compared to the Clear baseline context (because F0 carries greater perceptual weight); (2) in the Canonical, compared to the Reverse, context; (3) in the Canonical, compared to the Baseline Clear Speech context (because stimulus statistics exaggerate the dimension regularity in behavior).

High-gamma amplitude will be calculated using an approach that utilizes the Hilbert transform. Specifically, the signal will be filtered into 8 subbands, logarithmically spaced between 70-150 Hz. For each subband, we will calculate the amplitude (absolute value) of the analytic signal, which is estimated using the Hilbert transform. Each subband will be normalized to its baseline mean and standard deviation, estimated across trials. The HGA estimate is then the mean across these subbands.

We will use *least-squares linear regression neural encoding models* to investigate relationships between acoustic stimulus dimensions and STP neural responses during the baseline quiet context, in which stimuli sample a 2-d F0 x VOT grid. This approach will allow us to identify the subset of electrodes and temporal windows that encode at least one of these 2 dimensions at baseline; targeted analysis on this subset (described below) will then be used to compare listening contexts.

Encoding model inputs will consist of F0 and VOT, with an output of channel- and time-specific HGA. For a given electrode, individual models will be built using single trial data and a sliding window, allowing us to identify the temporal window relative to stimulus onset that yields significant models. Model quality will be assessed in two ways. First, using models built on all trials, we will calculate the regression *F*-statistic, which determines if any coefficients are significant. This will be compared to null distributions estimated with permutation tests that shuffle data across trials. Second, goodness-of-fit will be assessed for significant models by performing leave-one-out cross-validation and calculating R^2 , the proportion of variance in neural activity explained by the model. Finally, we will assess the relative encoding strength of each acoustic dimension using model coefficient *t*-statistics. In summary, this approach will allow us to identify the timing and anatomical location of F0 and VOT encoding during baseline quiet listening conditions for which dimensions are sampled orthogonally (as in **Figure 1a**).

To characterize shifts in neural encoding across listening contexts, we will investigate Noise using encoding models and Canonical/Reverse contexts using *cluster-based approaches*.^{32,49} Encoding models will be built from the Noise context for all channels and timepoints, using the same approach as Baseline. If a channel/timepoint is significant in either Baseline or Noise, the F0 and VOT coefficient *t*-statistics will be compared across contexts. We hypothesize that encoding of F0 will strengthen and VOT will weaken in Noise, as measured by changes in *t*-statistic magnitudes across multiple models. Next, we will compare neural responses for each of the two *Test* stimuli (which were embedded in the F0 x VOT grids, **Figure 1a**) between Baseline vs. Canonical and Canonical vs. Reverse. The clustering approach will look only at Baseline significant channels and time windows and involves randomly assigning listening context labels to single-trial data followed by a *t*-test at each time step. Across all permutations, a criterion value will be established for each timepoint (>95% of absolute value of *t*). For each of these permutations, we will next determine whether its value exceeds criterion across timepoints, and for how many timepoints it exceeds criterion (a 'cluster'). For each cluster, *t* values will be summed and assigned to all points in the cluster, with the largest summed cluster value stored for each permutation. This will create a null distribution of 1000 cluster values. We then will establish whether the cluster size calculated across real neural data (organized according to listening context) exceeds the 95% permutation-based cluster values such that $p < .001$ indicates an observed cluster is greater than all permutation-based clusters. Using this approach, we will identify context-dependent shifts in HGA responses, which we predict will reflect observed shifts in perceptual weights. Namely, we hypothesize that HGA responses in F0-encoding channels will be enhanced in the Canonical context relative to both Baseline and the Reverse context.

Rigor and Reproducibility. Analyses will be controlled for multiple comparisons, with sex as a co-variate in our analyses. We will use pre-registration and provide access to all the deidentified source data.

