## Study Design

### 1. Total number of subjects to be enrolled at this site (enter -1 for chart reviews, banking, registries):

25

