### 2. Describe and explain the study design:

This experimental study uses a within-subjects design.

All enrolled participants will be implanted with sEEG electrodes in the auditory cortex based on clinical necessity. During the post-operative period, patients will complete self-paced blocks of trial stimuli by listening to sound via earphones and making behavioral, categorical decisions about speech sounds, duration of stimuli, and pitch of stimuli. Simultaneous sEEG and scalp EEG recordings will be obtained to record neural responses to stimuli.

Participants will first complete a block of stimuli for clear speech to establish a baseline. They will then complete blocks of stimuli with experimental manipulations. All blocks will consist of intermixed exposure trials and test stimuli. Each participant will complete all tasks provided they are willing to do so and that their medical status permits.

Auditory stimuli used in this part of the study are part of the dimension-based statistical learning (DBSL) paradigm developed and extensively tested by [name] in previous research.

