### 3. Provide a description of the following study timelines:

#### Duration of an individual subject's active participation:

Participants will continue to be enrolled in the study for the duration of their sEEG implantation in the EMU. This period of time may range from 3-10 days post-operatively until the participant completes all research tasks, indicates that they would like to disengage from research activities, or is taken back to the operating room for removal of electrodes.

Each participant will have active participation in the study for only the amount of time per day that they voluntarily desire participating. Blocks of stimuli are self-paced and the research team will offer breaks between blocks as needed or requested by the participant.

Based on previous research with similar protocols and stimulus paradigms, we anticipate that a subject may complete all research tasks over a cumulative period of 2-3 hours. This includes equipment setup and removal.

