#### Duration anticipated to enroll all subjects:

This is a two year study. Based on historical volume of patients with similar inclusion criteria within PI [name]'s clinical practice, it is anticipated that the desired number of participants (n=25) will be enrolled within the first year. Should enrollment be lower than anticipated after Year 1, the enrollment period will be extended into Year 2.

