## Research Activities

### 1. \* Provide a detailed description of all research activities (including screening and follow-up procedures) that will be performed for the purpose of this research study. This description of activities should be complete and of sufficient detail to permit an assessment of associated risks. [?](#)

The participants in this study will be 15-25 year-olds undergoing stereoelectroencephalography (sEEG) implantation in the STP for clinically necessary localization of epilepsy foci or language mapping. Enrolled participants will not meet any exclusion criteria. The study will only be conducted if the subject's medical condition permits and if the subject is willing to participate and continue.

Personnel performing the research procedures will be suitably trained research staff.

All research activities will take place at UPMC Children's Hospital of Pittsburgh (CHP). After the clinically necessary sEEG electrodes are placed, patients will be monitored in the acute inpatient setting of the epilepsy monitoring unit (EMU). The EMU offers a fully staffed team of clinicians who will ensure the health of the patient. When patients feel well enough, they will be approached with the opportunity to participate in the proposed research by engaging in behavioral tasks and screening assessments. Participants will have up to 64 scalp electrodes placed at the completion of the surgical procedure to obtain scalp EEG recordings for research purposes. Scalp electrodes will come from the study team's own equipment inventory and will be covered by the head dressing applied to all sEEG patients post-operatively. These electrodes will remain on the scalp until the completion of sEEG recording or upon a participant's withdrawal from the study. sEEG and EEG recordings will occur simultaneously during behavioral tasks.

All clinical decisions, including placement of sEEG electrodes, will be made by the patient's clinical team based solely on medical necessity and benefit. [name] will obtain consent for the surgical procedure to implant sEEG electrodes in a separate process after an extensive clinical evaluation to determine medical utility of the surgery and discussion of risks and benefits involved.

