All potential subjects will be patients of [name] and the CHP neurological surgery service, who will decide when and if the patient is medically able to participate in research activities. All research-specific activities will be stopped at the request of the patient, patient's parents, or medical team. It will be made clear to patients and parents that participation is entirely voluntary and that patients or parents may make the decision to discontinue involvement in the study at any time.

Prior to completing research activities described below, participants will complete a 5-minute hearing screening via headphones by providing click responses on a computer. The hearing screening will be completed remotely within the participant's home and will be hosted and accessed on the Gorilla experiment platform ([gorilla.sc](http://gorilla.sc)). The research team will meet briefly with participants via Zoom on a non-recorded video call to provide instructions and guidance on accessing and completing the screening. Participant responses will be recorded directly and saved in a database on the Gorilla platform. This screening will occur prior to sEEG implantation.

Participants will also participate in a brief (~12-15 minute) language screening that evaluates phonological awareness. Participants will listen to single-word or single-letter speech stimuli played from a laptop, and provide verbal responses that require them to add, subtract, or blend sounds within a word. This screening procedure will occur in-patient following sEEG implantation but prior to the activities described below which involve neural recordings.

Neither screening procedure will be used for the purposes of determining eligibility.

Each participant will complete self-paced blocks of stimuli that will first establish a baseline for neural activity and behavioral responses with clear speech, and will then record responses for experimentally manipulated blocks to introduce 1) speech-in-noise and 2) a Canonical-Reverse block to model an "accent." Each block involves listening to sound via earphones and making a categorical decision between initial consonants (/b/ or /p/) by tapping a button to indicate the word heard by the participant.

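### Does enrolling exactly the 25 patients that the power calculation calls for leave the trial short if some do not finish?

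*SAP*

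**What the plan says.** The SAP, under Power and Sample Size, takes behavioural effect sizes from a pilot figure (not reproduced in the text available) and uses them "to estimate the sample size required for a predicted power of 0.8 (two-tailed alpha at .05) yields a sample of N=25". It treats neural power separately and less formally: it cites clear EEG effects in a pilot of 23, the better signal-to-noise ratio of sEEG, and the within-patient, within-electrode design.

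In the Protocol, Study Design item 1 ("Total number of subjects to be enrolled at this site") is answered with 25. Item 3 repeats the figure: "it is anticipated that the desired number of participants (n=25) will be enrolled within the first year". It adds: "Should enrollment be lower than anticipated after Year 1, the enrollment period will be extended into Year 2". There is one site ("All research activities will take place at UPMC" Children's Hospital of Pittsburgh), so 25 is the whole sample.

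Completion is conditional. Study Design item 2 says: "Each participant will complete all tasks provided they are willing to do so and that their medical status permits". Item 3 allows participation to end when a patient "indicates that they would like to disengage from research activities" or has the electrodes removed. Under Research Activities, the clear-speech baseline is recorded first, and the study "will then record responses for experimentally manipulated blocks to introduce 1) speech-in-noise and 2) a Canonical-Reverse block". The SAP likewise describes completion of all tasks by the same patient as a goal.

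Under Rigor and Reproducibility the SAP promises control for multiple comparisons, without naming a method or a family of tests.

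**The concern.** Read together, these statements suggest a sample size with nothing in reserve. If 25 is the number required for power 0.8, and 25 is also the number enrolled, then any patient who stops before the manipulated blocks lowers power for a contrast that needs those blocks. The order of blocks sharpens the point, because an early stop loses Noise and Canonical-Reverse, not the baseline. The Year 2 extension is triggered by slow enrolment, not by incomplete patients, and neither document states an inflation factor or a replacement rule.

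Multiplicity seems to push the same way: the calculation uses .05, yet the analyses are to be adjusted. At stake would be a missed behavioural shift. Because the neural predictions are read against that shift, their interpretation would weaken too.

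**Working it through.** **Inputs from the documents.** Power 0.8, two-sided alpha .05 and N = 25 (SAP, Power and Sample Size); enrolment 25 (Protocol, Study Design items 1 and 3); within-subjects design (item 2). The text gives no numerical effect size, no test and no loss rate.

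**1. The plan's own figure.** N = 25 cannot be derived forward without the effect size, so I solved for the effect it implies. *Assumption:* a paired t-test with standardised mean difference dz. Power is P(T > t(0.975, n−1)), where T is noncentral t with n−1 degrees of freedom and noncentrality dz·√n.

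- n = 25 gives 0.80 at dz = 0.584.
- n = 24 gives 0.80 at dz = 0.597.

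So 25 is the smallest sufficient n for dz from 0.584 to just under 0.597.

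**2. Fewer completers, complete cases only.**

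| Completers | Power, dz 0.584 | Power, dz 0.597 |
|---|---|---|
| 25 | 0.800 | 0.817 |
| 24 | 0.782 | 0.800 |
| 22 | 0.743 | 0.761 |
| 20 | 0.698 | 0.717 |

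**3. Assumed loss rates.** With 25 enrolled and binomial loss, expected power at dz 0.584 is 0.777 at 5% loss, 0.752 at 10% and 0.695 at 20%. At dz 0.597 it is 0.795, 0.770 and 0.714. These rates are illustrations; the documents supply none. To expect 25 completers, enrolment would be 25/(1 − loss):

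- 5%: 25/0.95 = 26.3, so 27
- 10%: 25/0.90 = 27.8, so 28
- 20%: 25/0.80 = 31.25, so 32

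That is 2 to 7 more patients.

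**4. Partial data under the planned model.** The SAP's Behavioral Analyses make patient a random effect, with block, F0 and their interaction fixed. Where baseline is one level of block, a baseline-only patient still informs the baseline F0 slope. *Assumptions:* linear approximation, equal trials per block, and no patient-specific F0 slope. The variance of the interaction is then proportional to 1/25 + 1/m, with m patients in the manipulated block, against 2/25 when all complete. Power is Φ(2.80·√[(2/25)/(1/25 + 1/m)] − 1.96); the complete-case version is Φ(2.80·√(m/25) − 1.96).

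| m | Complete cases | Using partial data |
|---|---|---|
| 24 | 0.78 | 0.79 |
| 22 | 0.75 | 0.77 |
| 20 | 0.71 | 0.75 |

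For m = 20: 1/25 + 1/20 = 0.09; √(0.08/0.09) = 0.943; 2.80 × 0.943 − 1.96 = 0.68; Φ = 0.75. About half of the loss is recovered.

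**5. Which effect was sized?** The SAP refers to behavioural effect sizes in the plural and names no contrast. If the limiting one is a perceptual weight in quiet (Aim 1), only the first block is needed, and losing later blocks costs it nothing.

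**6. Multiplicity.** With 25 completers at dz 0.584, power for the sized contrast runs from 0.80 (a single test, or Holm with much larger companion effects) to 0.64 (Bonferroni over three tests). The documents do not place any behavioural test in a family, so the range starts at no loss.

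**The case for a change.** The strongest case for acting is that the direction needs no effect size. On the SAP's own wording, fewer than 25 patients with the necessary blocks means less than the power claimed at N = 25. Losing at least one is likely even at a low rate: 1 − 0.95^25 = 0.72 at 5%. The recovery in step 4 also depends on the model. It shrinks if patients differ in their F0 slopes and those slopes are modelled, and it does not apply to a comparison of Canonical with Reverse alone. Stating an allowance would cost only words.

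The direction stands for a between-block contrast. What does not stand is the step to a shortfall that needs correcting. It requires a loss rate and a sized contrast that the documents do not give, and silence on replacement does not forbid it. The conditional wording is ordinary language about voluntary participation and predicts no particular attrition. The Protocol expects all tasks to take two to three hours in total, self-paced with breaks, within 3 to 10 days after surgery. At 5% loss the drop is about two points, and the upper end of the implied effect range still gives 0.80 with 24 completers.

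**Conclusion.** The observation is accurate: 25 required, 25 enrolled, and no stated margin. It does not call for a change. For a between-block contrast, a few early stops would cost modest power: from 0.80 to about 0.78 with one lost and about 0.70 with five lost, by complete-case paired t-test, and less where the mixed model uses partial data. These figures assume that N = 25 was set by such a contrast with dz between 0.584 and 0.597. Whether power falls below 0.8 cannot be determined from the documents, and no multiplicity shortfall is established.

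Nothing in the planned analyses becomes invalid with fewer completers; estimates are somewhat less precise. The one change that would raise power, enrolling 2 to 7 more patients at the assumed loss rates, draws on a scarce group implanted for clinical reasons at a single hospital. That is a poor trade against a loss of unknown and possibly negligible size. Accepting 25 is a fair choice. Stating whether 25 means enrolled patients or completers, and for which contrast, would help readers, but analysts can report the number contributing to each contrast without amending the plan.

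### The SAP sets H6 (plasticity in HG) against H7 (only at higher levels) but plans no regional comparison, so H7 could rest only on a non-significant result in HG

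*SAP*

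**What the plan says.** **Hypotheses (SAP, Analyses).** Recording across the supratemporal plane (STP) is said to allow "testing the strong, and falsifiable, hypothesis" that "adaptive plasticity effects are present in HG versus" (H6) being "apparent only at higher levels of the cortical hierarchy" (H7). Sites outside the STP serve as controls and for secondary hypotheses; no test is defined for them.

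**Neural tests (SAP, Neural Analyses).**
- Encoding models: "For a given electrode, individual models will be built using single trial data and a sliding window". The inputs are F0 and VOT. Anatomical location is to be identified for baseline quiet listening.
- Noise versus Baseline: models are fitted for every channel and timepoint. Coefficient t-statistics are compared wherever either context is significant, and the prediction is judged over several models with no split by region.
- Baseline versus Canonical, and Canonical versus Reverse: "The clustering approach will look only at Baseline significant channels and time windows", and its null distribution comes from "randomly assigning listening context labels to single-trial data".

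**Sample size (SAP, Power and Sample Size).** N=25 comes from behavioral pilot effect sizes. The SAP then says "This leaves open the issue of power for neural measures" and fills the gap with a scalp EEG pilot (N=23), the signal-to-noise advantage of sEEG, sEEG pilot data (a figure not shown) and the within-electrode design. It concludes that these "suggest that this sample size will be more than sufficient for sEEG measures, especially as they will be utilized in a within-patient/within-electrode experimental design".

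**Coverage (Protocol).** Every participant has auditory-cortex electrodes (Study Design, items 2 and 4), and Research Activities describes implantation in the STP. Placement is decided on clinical need alone. Nothing assures HG contacts, or HG and higher contacts in the same patient.

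**The concern.** H6 is an existence claim, and a test within HG channels can establish it. H7 has two parts: an effect at higher sites and no effect in HG. The planned tests can show the first part. The second could come only from HG channels failing to reach significance. Significance in one region and not in the other is not evidence of a difference between them, and still less of absence in one.

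An HG null has other possible sources. Few HG contacts may accrue. In the Canonical/Reverse analysis, a channel that is not significant at Baseline is never tested. At stake is the anatomical conclusion that the SAP presents as what sEEG makes possible: it could reflect where electrodes were placed rather than where the cortex adapts.

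**Working it through.** The documents give no trial counts, channel counts per region or neural effect size in the text. Steps 2 to 7 therefore rest on assumptions and show ranges.

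**1. The plan's own figure.** N=25 (power 0.80, two-tailed .05) cannot be reproduced, because the effect size is in a figure not shown and the test is not named. Solving backwards for a paired test: (1.960 + 0.842)/√25 = 0.560 SD (normal), or 0.584 SD (noncentral t). The 0.584 is used below only as a yardstick.

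**2. What sets power within one electrode.** For m trials per context and single-trial effect d, power ≈ Φ(d√(m/2) − 1.96). At d = 0.3:
- m = 40: Φ(1.342 − 1.96) = 0.27
- m = 200: Φ(3.00 − 1.96) = 0.85

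Patient count is not an input here. It enters the regional question through the number of HG and higher channels that accrue.

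**3. False pattern, one test per region.** Let the true effect be equal in both regions, so H7 is false. With independent tests, P(higher significant, HG not) = p_higher × (1 − p_HG):
- 0.8 × 0.2 = 0.16
- 0.8 × 0.5 = 0.40
- 0.95 × 0.05 = 0.05

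Positive dependence between regions would lower these.

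**4. False pattern, any-channel rule.** With per-channel power 0.3, 20 higher channels and k HG channels, P = (1 − 0.7^20) × 0.7^k: 0.34 (k = 3), 0.17 (k = 5), 0.03 (k = 10).

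**5. Simulation with multiplicity adjustment.** The SAP promises control for multiple comparisons but names no method, so two are shown. Set-up: 25 patients; channel z = common mean + patient effect (SD 0.5) + channel effect (SD 0.5) + N(0,1); same mean in both regions; any-channel rule after adjustment over all channels; 1,500 runs.

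| Coverage | Mean z | Bonferroni | Benjamini-Hochberg |
|---|---|---|---|
| 1 HG channel in 10 patients, 4 higher in all 25 | 1.0 | 0.70 | 0.51 |
| same | 1.5 | 0.58 | 0.14 |
| same | 2.0 | 0.30 | 0.01 |
| same | 3.0 | 0.02 | 0.00 |
| 1 HG channel in 15 patients, 4 higher in all 25 | 1.5 | 0.46 | 0.07 |
| 2 HG and 2 higher in all 25 | 1.5 | 0.07 | 0.01 |

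**6. A direct regional test.** In the same runs, a paired patient-level test (two-sided .05) wrongly favoured higher sites 0.017 to 0.035 of the time, against a nominal 0.025. That protection needs a comparable effect scale. With 2 + 2 channels in all 25 patients and mean z of 2.1 in HG against 3.0 at higher sites, from lower HG signal-to-noise alone, a direct test on z favours higher sites about 0.97 of the time. At 0.80 power the detectable within-patient difference is 0.58 SD (25 patients with both regions), 0.78 SD (15) or 1.00 SD (10).

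**7. Chance of reaching a true H7 under a sound rule.** Take 25 patients with both regions, a higher-site effect of 0.584 SD and an HG effect of zero. Require a significant regional difference and an upper 95% limit for HG below the margin.
- Margin 0.584: about 0.48 (correlation between regions 0) to 0.68 (correlation 0.5).
- Margin 0.292: about 0.25 to 0.27.

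**The case against.** The strongest reply is that H6 is a claim of presence: one valid positive HG result supports it and refutes H7, with no regional contrast needed. That stands. A reader might also infer that the study will declare HG non-adaptive from a null. The SAP never says so; the point is that it offers no other route to H7 and no rule for an HG null.

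Three further readings go too far:
- *That N=25 is irrelevant to the neural tests.* This is true of a single electrode, but not of the regional pattern: step 5 changes with the number of patients who have HG contacts.
- *That Baseline selection is biased against HG.* It applies to both regions alike and only to the cluster test; the Noise models cover all channels. It can thin HG coverage, but does not by itself favour an HG null.
- *That the sufficiency statement has nothing behind it.* The SAP cites scalp EEG and sEEG pilot data, signal-to-noise and design. This support is qualitative, and none of it addresses a comparison of regions.

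Finally, the pre-registered analyses and the proposal's Approach section, to which the SAP refers, were not supplied. A regional test may be there. What can be said is that this SAP does not contain one.

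**Conclusion.** The concern holds for H7, not for H6. As written, the SAP has no test that could separate plasticity only at higher sites from plasticity in both regions with too little HG information to detect it. With equal true effects, the false pattern occurs between about 0 and 0.7 of the time. The high end needs sparse HG coverage, weak effects and an any-channel rule with adjustment over all channels; none of these is stated in the plan. With two HG channels in every patient, or large effects, the problem nearly disappears. The size is therefore uncertain, but the gap in the inference does not depend on it. The sufficiency statement may be reasonable for within-electrode tests; it does not extend to the HG-versus-higher comparison.

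**What to change.** For each context contrast (Noise vs Baseline, Canonical vs Reverse, Canonical vs Baseline):

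1. Add a region (HG vs higher STP) by context model with patient as a random effect and channels nested in patient, or a patient-level permutation test in patients with both regions.
2. Pre-state an effect scale that is comparable across regions and is not the t or z statistic, for example the high-gamma context difference relative to the channel's own Baseline stimulus response.
3. Report the regional difference and the HG effect, each with a 95% confidence interval.
4. Use one anatomical channel rule in both regions, with the Baseline-selected version as a sensitivity analysis.
5. State the decision rule. A significant regional difference supports a larger effect at higher sites. Concluding that it occurs only there also requires the HG interval to exclude a pre-stated smallest effect of interest. Otherwise, unless HG itself shows an effect, report H6/H7 as unresolved. Never conclude H7 from a non-significant HG result alone.
6. Report patients and channels per region, and limit the sufficiency statement to the within-electrode tests.

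If the pre-registration or the Approach section already holds a regional test, carry it into the SAP.

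**Cost.** One added model per contrast on data already recorded; no change to patients, tasks or placement. Including channels that do not encode at Baseline may dilute the effect, hence the sensitivity analysis. The real price is that an unresolved outcome is likely even if all 25 patients have both regions: under step 7's assumptions a true H7 is reached only about 0.25 to 0.68 of the time, and less often with fewer such patients.
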